temporal EEG leads. The lesser involvement of medial temporal structures with the seizures induced by FEAST should result, in turn, in lesser amnestic effects, especially for autobiographical information ([name] et al., 2000a). To accomplish this we propose to compare matched groups of patients who have elected to receive FEAST to non-randomized patients received regular treatment with ultrabrief right unilateral (UB RUL) ECT. Since FEAST delivers an ultra-brief stimulus and an identical titration schedule is used in both groups, the only difference in the stimulation given between the groups will be the features unique to FEAST, i.e., the use of unidirectional stimulation and geometry and positioning of the electrodes. As we will carefully evaluate efficacy, this comparison will provide preliminary (but not definitive) data on whether efficacy is equivalent for FEAST relative to traditional ECT.

In summary, we are confident that FEAST does not increase the risks of ECT. It is simply a form of ECT that is more focal and likely more efficient in seizure induction. We have optimized FEAST's potential for being efficacious by limiting its degree of focality and ensuring that markedly suprathreshold electrical dosage can be administered. By using 1.25" diameter electrodes rather than the earlier 3/4" electrodes, we have demonstrated acceptable impedances and have had no instances of skin burns.

D.3 Titrating in the Current Domain

Another innovation was originally examined in this study. This modification was the use of current or pulse amplitude as the basis for titrating electrical dosage to the patient's seizure threshold. As explained below, we no longer use procedures for titrating in the current domain as part of this study. Our original rationale for this approach and the reasons we no longer include it in the procedures are explained below.

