Across the sites 60 patients will be enrolled to achieve 40 FEAST patients who will fully complete this study at the MUSC Institute of Psychiatry, Brain Stimulation Service (BSS) in Charleston, SC, and at GRU in Augusta, GA and Aiken, SC. At both MUSC and GRU, roughly matched 30 patients (each) will also be recruited from those scheduled to receive UB RUL ECT to obtain a cohort of 40 RUL comparison patients. The FEAST and UB RUL ECT groups must meet identical inclusion/exclusion criteria and will undergo identical evaluation procedures. The only difference between the groups will be that one receives FEAST and other UB RUL ECT. The treatment received by the UB RUL ECT group will not be affected by participating in this protocol. This is an open label, non-randomized, non-masked study. Separate consent forms will be used in each group. We are thus asking FDA permission to study 60 patients with FEAST. An additional 60 patients will be studied who receive conventional ECT. Even though they are getting conventional ECT, they are covered by this FDA IDE as their data will be used for comparison purposes with FEAST.

Patients will be selected from those referred for ECT for the treatment of major depressive episode. To verify diagnosis, the SCID-P will be administered to derive DSM-V diagnosis (unipolar or bipolar major depressive episode) and relevant subtypes and specifiers (American Psychiatric Association, 2013).

Inclusion and exclusion criteria are presented in Table 2. Briefly, patients will be between the ages of 18 and 90 years and will provide informed consent. Exclusions include: history of schizophrenia, schizoaffective disorder or any non-mood disorder psychosis, rapid cycling bipolar disorder, central nervous system illness other than conditions associated with psychotropic exposure, alcohol or substance abuse or dependence in the past 3 months, pregnancy, epilepsy, inability to have stable medications, and ECT within the past six months.

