Health-Related Quality of Life (HRQOL). We hypothesize that the reduced side effect burden of FEAST translate into a HRQOL advantage. We will use the Medical Outcomes Study SF-36 (MOS SF-36) (Ware and Sherbourne, 1992). While there are depression-specific HRQOL scales (Grégoire et al., 1994, Turner, 1994), the MOS SF-36 was selected because of its widespread use (including treatment studies of MDD) (Lonnqvist et al., 1995, Lonnqvist et al., 1994), brevity, data on reliability and validity (McHorney et al., 1993), and its sensitivity to change with the treatment

of MDD (Miller et al., 1998). Its 8 dimensions have internal reliability estimates ranging from .77 to .98, and strong relative precision values compared to the full scale. The MOS SF-36 is completed at preECT baseline, and during the week following ECT. [name] has shown that ECT samples are especially impaired in MOS SF-36 scores at baseline, and that sustained remission following ECT results in profound improvement, with scores of remitted patients virtually indistinguishable from normative values (Rosenquist et al., 2006, McCall et al., 2013, McCall et al., 2011b, McCall et al., 2006).

Expectations and Attitudes Toward Treatment. A structured interview is conducted at baseline and during the week following FEAST/ECT. At baseline, this interview queries expectations regarding the effects of the impending course on mood and cognition. The postECT interviews is structured to make the same inquiries about the completed ECT course. Patients provide a global self-evaluation of the impact of the treatment on mood and memory using a 9-point Likert-type scale (i.e., +4 very much improved, 0 no change, -4 very much worsened. Post-ECT patient reports using this interview have shown strong relations with clinical outcome, extent of retrograde amnesia, and treatment modality (Brakemeier et al., 2011a, Berman et al., 2008).

B.11 Documentation of Adverse Events

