The primary analysis for Hypothesis 4 will use all available HRSD₂₄ data (i.e., the intent-to-treat data) from the FEAST and UB RUL ECT samples. A random regression model will be used to examine the relationship between HRSD₂₄ scores and treatment group. Time will be the within-subjects repeated measures factor, site and treatment group the between-subjects factors, with medication-resistance classification and baseline HRSD₂₄ serving as covariates. All interactions with time will be modeled. In secondary analyses, we will also include age, gender, age-at-onset of illness, and duration of current episode as covariates, if pre-screening indicates utility. We will investigate whether HRSD₂₄ scores are linear in time or quadratic, cubic, or piece-wise linear (e.g., hockey-stick shaped). Indeed, in a study comparing several different statistical methods in their sensitivity to ECT treatment groups differences in rate of clinical improvement, we found that the HRSD₂₄ scores over time were frequently nonlinear (Nobler et al., 1997a). The type of analysis conducted on HRSD₂₄ scores will be repeated for secondary analyses with the MADRS, IDS-SR, and CGI-S.

FEAST and UB RUL ECT will also be compared in the categorical outcomes of final remission status (HRSD₂₄ of 10 or less at post-treatment) in a secondary analysis to gauge generality of the effect and clinical significance. Nominal logistic regression analysis will be used to compare the treatment groups in covariate-adjusted odds of remission. Remission status will be the dependent variable. The independent variables will be the treatment group indicator, along with site, medication resistance, and baseline HRSD₂₄.

Hypothesis 5. In two primary cognitive measures, orientation recovery time and CUAMI-SF scores, FEAST will have a significant advantage relative to UB RUL ECT.

The cognitive measures were described in Section B.12. Orientation time will be averaged within each patient across all treatments. An ANCOVA will be conducted on these values with Site and Treatment Group as between-subject factors, and age and number of treatments in the average as covariates. A similar ANOVA will be conducted on CUAMI-

SF scores, with Site and Treatment Group as between-subject factors, and age, number of treatments, and baseline CUAMI-SF score as the covariates.

Hypothesis 6. FEAST will have a significant advantage in the subjective global evaluation of the effects of ECT on memory.

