An ANCOVA will be conducted on scores at the postECT time point. Site and Treatment Group will be the between-subject factors and age, percentage change in HRSD₂₄ scores and percentage change in CUAMI-SF scores will be covariates..

C. Risk Analysis

It is now clear that with our experience in 35 patients, that FEAST is a relatively well tolerated procedure. Our preliminary data suggest that its cognitive side effect profile is equal if not lower than one observed with ultrabrief pulse right unilateral ECT. In turn UB RUL ECT is now a widely, internationally used ECT modality. It is established to have a superior risk profile compared to traditional forms of ECT using bilateral or bifrontal electrode placement and/or brief pulse or sine wave stimulation (Loo et al., 2008, Loo et al., 2011, Loo et al., 2012, Loo et al., 2013, Loo et al., 2007, [name] et al., 2008). Thus, this study contrasts an established ECT modality with a superior side effects profile (UB RUL ECT) to an experimental treatment (FEAST) that is expected to have a further improved side effect profile.

C.1 Risks of Evaluation Procedures

The research evaluation procedures include interviews to determine diagnosis and psychiatric symptomatology, medical exams, cognitive tests, self-report questionnaires (depressive symptoms, function, subjective evaluations of mood and memory effects, etc.), electrophysiological measures (ictal EEG), and fMRI measures. These evaluation procedures involve no risks to subjects.

C.2 Risks Unique to FEAST

The major risks of the research, beyond those associated with ECT in general, are those associated with the administration of FEAST. This new modality is a form of ECT and is expected to have reduced risk of cognitive impairment compared to traditional forms of ECT. In particular, the use of a 0.3 ms pulse width is thought to markedly reduce the side effects of traditional brief pulse ECT, without impact on efficacy ([name], 2004a, [name] et al., 2008, Loo et al., 2012). Furthermore, the FEAST condition will be administered in such a way that cognitive side effects should be less intense and/or persistent than that which regularly occurs with older methods that do not take into account variation in seizure threshold. The use of a unidirectional current and focal stimulation should additionally contribute to further reductions in cognitive side effects.

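### Hypothesis 6 compares an unmasked self-rating of memory between non-randomized groups without adjusting for the baseline expectation that the same interview collects

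*Combined protocol and SAP*

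**What the plan says.** Section IV.B.15 states Hypothesis 6 as "FEAST will have a significant advantage in the subjective global evaluation of the effects of ECT on memory". The test is an ANCOVA on the post-course score, and its terms are given as "Site and Treatment Group will be the between-subject factors and age, percentage change in HRSD₂₄ scores and percentage change in CUAMI-SF scores will be covariates". The same section says that the primary analyses test the listed hypotheses, and Hypothesis 6 is one of them.

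The outcome is described in section IV.B.10: "Patients provide a global self-evaluation of the impact of the treatment on mood and memory using a 9-point Likert-type scale". The scale runs from +4 (very much improved) through 0 to -4 (very much worsened). The same paragraph says of the structured interview: "At baseline, this interview queries expectations regarding the effects of the impending course on mood and cognition". It adds that the post-course interview asks the same things about the completed course. Table 3 lists the ECT Attitude Interview in the pretreatment battery, and section IV.B.1 requires identical evaluation in both groups.

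On design, section IV.B.1 says "This is an open label, non-randomized, non-masked study". Section III.D.2 proposes to "compare matched groups of patients who have elected to receive FEAST to non-randomized patients" on usual UB RUL ECT. Section IV.B.1 says the comparators are "recruited from those scheduled to receive UB RUL ECT".

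**The concern.** The outcome is a patient's opinion, given by someone who knows which treatment was received. Such a rating may depend partly on what the patient expected beforehand. The two groups are formed by different routes, so their expectations may differ before the first treatment.

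The plan collects a measure of that expectation in both groups and then does not use it. The two change-score covariates capture mood improvement and objective memory change; neither captures prior belief. If expectation differs by group and is related to the post-course rating, the Hypothesis 6 group term mixes an effect of FEAST on perceived memory with a difference that existed before treatment. Section IV.B.15 wants to protect the Type I error rate and to supply effect sizes for a later randomized study, and a biased group term would serve neither aim.

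**Working it through.** **Is expectation handled anywhere?**

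- Hypothesis 6 model (IV.B.15): site, group, age, percentage change in HRSD24, percentage change in CUAMI-SF. Expectation is absent.
- Matching (study overview just before section B, Protocol): gender, unipolar or bipolar diagnosis, age, baseline mMMS. Expectation is absent.
- Baseline screen at P < 0.2 (IV.B.15): sociodemographic and clinical features. Expectation is not named, and no rule says what follows from a difference. Table 3 lists the interview under a separate heading for patient attitudes.
- By contrast, the Hypothesis 4 model includes baseline HRSD24, and the Hypothesis 5 model for CUAMI-SF includes baseline CUAMI-SF.

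**How large could the bias be?** The plan gives no SD, correlation, expectation difference, power or test alpha for Hypothesis 6, so there is no figure to reproduce. What follows is illustrative.

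- From the documents: 40 FEAST patients (study overview) and 40 comparators (IV.B.1).
- Assumed: two-sided alpha 0.05; no true effect; correlation r between baseline expectation and the post-course rating of 0.2 to 0.5; a group gap in expectation of 0.3 to 0.8 SD.

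If expectation is omitted and unrelated to the other covariates, bias = r × gap. The standard error is √(2/40) = 0.224 SD. The chance of rejecting is Φ(bias/SE − 1.96) + Φ(−bias/SE − 1.96). For r = 0.3 and a gap of 0.5 SD, bias = 0.15 SD and 0.15/0.224 = 0.67, so the chance is Φ(−1.29) + Φ(−2.63) ≈ 0.103.

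A simulation of the planned ANCOVA checked the approximation. It had 4,000 runs per cell and was run twice, with a site-by-group term. The two change scores were independent of expectation, each with coefficient 0.3. The last two columns add the expectation covariate, measured exactly or with reliability 0.7.

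| r | Gap (SD) | Bias (SD) | Approximation | Planned ANCOVA | Adjusted, exact | Adjusted, reliability 0.7 |
|---|---|---|---|---|---|---|
| 0.2 | 0.3 | 0.06 | 5.8% | 5.2-5.8% | 5.4% | 4.3% |
| 0.3 | 0.5 | 0.15 | 10.3% | 10.5-11.4% | 6.0% | 5.3% |
| 0.5 | 0.5 | 0.25 | 20.1% | 21.0-22.4% | 5.6% | 6.0% |
| 0.5 | 0.8 | 0.40 | 43.2% | 48.0-48.7% | 5.4% | 9.6% |

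The exact covariate brings the bias to about zero. With reliability 0.7, residual bias across all cells with a gap is about 0.02 to 0.12 SD. For scale, 40 per group has 80% power for (1.96 + 0.84) × 0.224 ≈ 0.63 SD.

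**What adjustment leaves.** With an added 0.3 SD effect of unmasked reporting after the course (r = 0.3, gap 0.5 SD, no true effect), the planned model shows 0.46 SD and rejects in 59% of runs. The adjusted model still shows 0.31 SD and rejects in 32%.

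**The case against.** The best defence is that the plan is candid. The study overview says the groups are only loosely matched and the cognitive comparison is a rough one. Section IV.B.5 puts efficacy and side effects behind the EEG aim, and IV.B.15 calls the study preliminary. This lowers the consequence. It does not explain leaving out a response already collected for a hypothesis that IV.B.15 places among the primary analyses.

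Three further objections stand and limit the point:

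- The 9-point scale is described for the post-course rating. The baseline questions concern mood and cognition, and a numeric memory-specific baseline score is implied by the parallel interviews but not stated.
- Adjustment does not touch reporting bias that arises after treatment.
- The model also conditions on two post-treatment changes, so even the adjusted group term is not the total effect of FEAST on perceived memory.

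A reader might infer that the bias must favour FEAST, because the protocol expects FEAST to spare memory. That is the investigators' expectation, and the documents do not record what patients believe. UB RUL ECT is itself presented as the ECT form with the fewest cognitive effects (IV.C.5), so comparators may be optimistic too. Those who elect FEAST may be the ones most worried about memory.

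A reader might also push the inputs further: r = 0.5 with a 1 SD gap gives 0.50 SD and about 60%. Nothing in the documents supports those values. Nor did both groups choose their treatment in the same sense, since only FEAST patients are said to have elected it. The item is also not purely a rating of harm, because it runs in both directions.

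**Conclusion.** The omission is real and worth correcting, but modest. Hypothesis 6 leaves out a baseline expectation response taken in both groups of an open-label, non-randomized comparison, although Hypotheses 4 and 5 (CUAMI-SF) adjust for their own baselines. Any group difference in prior expectation that is related to the rating would bias the group term.

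Direction and size cannot be learned from the documents. A gap favouring FEAST could create an apparent advantage; a gap the other way could hide a true one. The range of about 6% to 48% rests wholly on the assumed correlation, gap and alpha. That a claim of FEAST advantage would be sound once expectation is adjusted for is also not supported, because the rating stays unmasked.

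**What to change.** Before analysis, confirm that the ECT Attitude Interview records a numeric baseline expectation for memory or cognition. Then amend Hypothesis 6 in section IV.B.15 as follows:

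1. Add the baseline expected-effect-on-memory/cognition score as a covariate in the ANCOVA.
2. Report that score by treatment group.
3. Base the Hypothesis 6 result on the expectation-adjusted group term.
4. Describe the result as exploratory, stating that adjustment addresses measured prior expectation but not unmasked reporting after the course.

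The cost is one degree of freedom and possibly an estimate less favourable to FEAST. If the item is already scored, only the analysis wording changes. If it is not, the baseline form would need a scored item.

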The measures of Clinical Status and Characteristics in Table 3 are essentially unchanged since the original IDE. The cognitive battery is considerably reduced. This was done since the primary goal of this study is the comparison of the groups in EEG manifestations of seizure, with comparisons of efficacy and side effects secondary. Second, none of the dropped measures showed significant change with FEAST administration in our prior analyses, and the literature on traditional ECT has only shown persistent deficits for retrograde memory for autobiographical events ([name], 2014b). The measures that were retained serve a particular purpose: (1) the mMMS at baseline is used for sample characterization and matching of the two groups. A significant difference between the groups would denote an effect pertaining to global cognitive status. This is not expected. (2) Orientation recovery will be assessed at each treatment (but obviously not at preFEAST baseline). This measure has been extremely sensitive to differences in ECT treatment modalities (sine wave vs. brief pulse; ultrabrief vs. brief pulse, BL ECT vs. RUL ECT, etc.) and has been found to predict long-term deficits in autobiographical memory (Sabin et al., 1995b). We expect the FEAST group to manifest faster recovery of orientation than the UB RUL ECT group, even though the latter has manifested remarkably rapid recovery compared to other ECT modalities ([name] et al., 2008). (3) The most critical measure is the CUAMI-SF. This measure has repeatedly shown differences between modalities and has the strongest evidence for persistent deficit following ECT. While effects of UB RUL ECT on this measure have been slight (compared to retested normal controls), nonetheless we predict an advantage for FEAST in this measure of autobiographical amnesia. (4) The Attitudes Interview collects patient self-report on the effects of the treatment course on mood

and memory. A global assessment is given by the patient, akin to a clinical global impression (CGI) for each domain. Recent research has shown that these are the only self-report measures in the history of ECT research to show significant covariation with objective cognitive deficits and with type of ECT modality (Berman et al., 2008, Brakemeier et al., 2011b). We predict that the FEAST and UB RUL ECT groups will be equivalent in self-report of effects on mood, but the FEAST group will report less deleterious impact on memory.

B. 5a MRI scan

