Oreintation recovery time will be assessed at every treatment session. The most profound cognitive effects of ECT are expressed in the postictal period (Daniel and Crovitz, 1983a, Daniel and Crovitz, 1983b, [name], 1986a). The repeated assessment (every treatment) strongly enhances reliability of measurement, and allows for examination of progressive change over the treatment course (Calev et al., 1991a, Calev et al., 1991b, [name] et al., 1986). The measurement of orientation recovery has been particularly sensitive to variation in ECT electrode placement, waveform, and dosage. Further, it has been repeatedly found to be a potent predictor of the degree of retrograde amnesia following the ECT course, even in the long-term (Sobin et al., 1995b). Following seizure termination, orientation (5 items) is assessed continuously until the criterion for full recovery is met or 90 min elapse. The critierion for recovery is correct response to 4 of the 5 items. The 5 questions pertain to name, birth date, age, place, and day of the week.

The mMMS, Buschke Selective Reminding Test (BSRT) and CUAMI-SF will be administered at baseline and at follow-up (during the week following FEAST or UB RUL ECT). The modified form of the MMS provides a total socre of 57 (as opposed to 30 with the original version) and broader coverage of gross cognitive abilities (Mayeux et al., 1981, Stern et al., 1987). The primary use of the mMMS is sample characterization, especially since there is evidence that low baseline scores predict more severe short- and long-term retrograde amnesia (i.e., cognitively-compromised paitents are more vulnerable to the key adverse effect on memory) (Sobin et al., 1995a). No change is expected in mMMS scores in either group. However, as a safety measure, the two groups will be compared in change in mMMS scores to verify this assumption and assure that there was no change in global congitive status.

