Anterograde verbal learning and memory will be assessed with the BSRT (Hannay & Levin, 1985). Impairments in verbal learning have been demonstrated with this instrument when administered during the ECT course, with impairments in retention (delayed recall) most evident shortly following the treatment course (Steif et al., 1986). BSRT scores during and immediately following ECT have been sensitive to differences in ECT electrode placement (e.g., [name] et al., 1993; [name] et al., 2007). Versions A and B (Hannay & Levin, 1985) will be used in an ABAB or BABA format over the 4 time periods, with assignment to either order randomly determined. The BSRT will follow standard scoring using a 6 trial acquisition phase, and free recall tested after a 30 min retention interval. Indeed, an invariant order of testing will be used at each time point, starting with the mMMS, then the 6-trial acquisition phase of the BSRT, followed by administration of the CUAMI-SF during the delay interval, followed by the free recall trial of the BSRT. The dependent measures derived from the BSRT will be total recall over the 6-trial acquisition phase (learning) and the delayed total recall score (retention). We expect that the FEAST group will have superior scores on the delayed recall score relative to the comparison group at the immediate postECT time point. We do not expect group differences at the later time points, since persistent deficits following ECT on this task have not been identified (e.g., [name] et al., 1993; [name] et al., 2007).

Retrograde amnesia for autobiographical information will be assessed with the CUAMI-SF (McElhiney et al., 2001). Although there has been some controversy about the reliability and validity of the measure (Semkovska and McLoughlin, 2010, Semkovska and McLoughlin, 2013, Semkovska et al., 2012{Semkovska, 2014 #23089}), the CUAMI-SF has been remarkably sensitive to both short- and long-term effects of ECT ([name], 2014a), showing, for example, long-term differences in amnesia scores as a function of electrode placement, stimulus waveform, and number of treatments ([name] et al., 2007, [name] et al., 2008). The CUAMI-SF is also the only neuropsychological instrument to show significant covariation with patients' subjective report of the effects of ECT on their memory (Berman et al., 2008, Brakemeier et al., 2011a). Accordingly, we expect post-course CUAMI-SF scores to be superior in the FEAST relative to the UB RUL ECT group.

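### The only Hypothesis 6 model adjusts for change in CUAMI-SF, a post-treatment outcome FEAST is predicted to improve, so its group term is not the unqualified advantage that H6 states (minor)

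*Combined protocol and SAP*

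**What the plan says.** Section IV.B.15 states Hypothesis 6 without any condition: "FEAST will have a significant advantage in the subjective global evaluation of the effects of ECT on memory". Section IV.B.5, describing the attitudes interview, makes the same prediction: "the FEAST group will report less deleterious impact on memory".

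One analysis is planned. It is an ANCOVA on the post-ECT rating with site and treatment group as factors. Age, percentage change in HRSD24 and "percentage change in CUAMI-SF scores will be covariates". No H6 model without CUAMI-SF change is planned, and no reason for the adjustment is given.

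On the covariate itself, the document says:
- It is measured after treatment. In IV.B.12, "CUAMI-SF will be administered at baseline and at follow-up", with follow-up in the week after the course.
- FEAST is expected to do better on it. IV.B.5: "nonetheless we predict an advantage for FEAST in this measure of autobiographical amnesia". IV.B.12: "we expect post-course CUAMI-SF scores to be superior in the FEAST relative to the UB RUL ECT group". Hypothesis 5: "In two primary cognitive measures, orientation recovery time and CUAMI-SF scores, FEAST will have a significant advantage relative to UB RUL ECT".
- It is related to what patients report. IV.B.12 calls CUAMI-SF the "only neuropsychological instrument to show significant covariation with" patients' own account of memory effects, and IV.B.10 links the interview ratings to the extent of retrograde amnesia.

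**The concern.** A group term adjusted for a variable that treatment is expected to change no longer measures the whole group difference. It measures the difference between patients with the same CUAMI-SF change. H6 does not ask whether FEAST patients report less memory harm than their objective amnesia would explain. It asks whether they report less harm.

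If Hypothesis 5 is true, part of the benefit named in H6 is credited to the covariate and leaves the H6 estimate. If FEAST were worse on CUAMI-SF, part of any reported harm would leave it in the same way. IV.B.15 lists subjective cognitive changes among the major areas of investigation and expects the study to yield effect sizes for powering a randomised trial. A conditional difference carried forward as the overall one would mislead that planning.

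**Working it through.** The documents give no effect size, SD or power for H6, so there is no planned figure to reproduce. The first step is a reading of the text; the second shows how large the shift could be.

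**Step 1: what the group term estimates.** Put both measures on a scale with within-group SD 1. Let dY be the total group difference in the self-rating, dM the group difference in CUAMI-SF change (positive when FEAST is better), and r their within-group correlation. In a linear ANCOVA:

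adjusted group difference = dY − r × dM

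This equals dY only if dM = 0, contrary to Hypothesis 5, or r = 0, contrary to IV.B.10 and IV.B.12. With both positive, as the protocol expects, the planned term is smaller than dY.

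**Step 2: size.** Inputs:
- 40 per group, the completer target for each cohort in IV.B.1.
- Assumed: dY = 0.5, two-sided 5%, r = 0.2, 0.4 or 0.6, and dM from 0 to 0.5.

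SE = √(1 − r²) × √(2/40) × √(1 + dM²/4), with power from the noncentral t distribution. Without the covariate, SE = √(2/40) = 0.224 and power is 0.60. For example, at dM = 0.1 and r = 0.4 the estimate is 0.5 − 0.04 = 0.46, SE is 0.205 and power is 0.60.

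| dM (SD) | Estimate at r = 0.2 / 0.4 / 0.6 | Power at r = 0.2 / 0.4 / 0.6 |
|---|---|---|
| 0 | 0.50 / 0.50 / 0.50 | 0.62 / 0.67 / 0.79 |
| 0.1 | 0.48 / 0.46 / 0.44 | 0.58 / 0.60 / 0.68 |
| 0.2 | 0.46 / 0.42 / 0.38 | 0.54 / 0.52 / 0.55 |
| 0.3 | 0.44 / 0.38 / 0.32 | 0.50 / 0.44 / 0.42 |
| 0.5 | 0.40 / 0.30 / 0.20 | 0.42 / 0.29 / 0.19 |

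Shrinkage at dM = 0.1 runs from 0.02/0.5 = 4% to 0.06/0.5 = 12%.

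**Step 3: like for like.** The planned model also contains percentage change in HRSD24. Assume it correlates 0.3 with the rating, is uncorrelated with CUAMI-SF change, and does not differ between groups (as Hypothesis 4 predicts). The residual SD becomes √(1 − r² − 0.09). Power is 0.64 without CUAMI-SF change. With it, power is 0.62 / 0.65 / 0.74 at dM = 0.1 and 0.54 / 0.48 / 0.47 at dM = 0.3.

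**Step 4: which rows are plausible.** III.C.5 and IV.C.3 report UB RUL amnesia scores that could not be told apart from those of healthy comparison subjects. IV.B.5 calls UB RUL effects on this measure slight. In the pilot (III.D.6), AMI-SF went from 53 ± 4.9 to 51.5 ± 5.1 with FEAST (p = 0.6). That is a within-group loss of 1.5 points, about 0.3 SD, and not a comparison with UB RUL. A comparator with little amnesia leaves little room for a large dM, so the upper rows are the more plausible.

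**Step 5: the reverse direction.** If FEAST were worse on CUAMI-SF by 0.1 SD, the H6 estimate would leave out r × 0.1 = 0.02 to 0.06 SD of reported harm.

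**The case against.** The strongest reply is that the conditional question is worth asking. Hypothesis 5 already tests CUAMI-SF directly, IV.B.15 lists objective and subjective changes as separate areas, and a model of self-report beyond objective amnesia and mood would add something new. That supports keeping the model as a secondary analysis. It does not support it as the only test of H6, because neither statement of the prediction carries such a condition. Where the plan does add a post-treatment covariate to study a relation, in Hypothesis 2f, it says so.

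The reply on size largely stands. The documents give no value for r, and it could be low between two ultrabrief right-sided treatments that both cause little amnesia. Decision weight is also limited: Section II does not name this rating, IV.B.5 ranks side effects behind the EEG comparison, and selection and expectation in an open, non-randomised study could exceed a shift of 0.02 to 0.06 SD.

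A reader might infer three stronger points that the documents do not support:
- *That the H6 test loses most of its effect or power.* The figures of 0.20 and 0.19 need a 0.5 SD group difference together with r = 0.6, and nothing in the documents supports that pair.
- *That memory harm would go unseen.* The Hypothesis 5 analysis would still estimate any CUAMI-SF difference.
- *That HRSD24 change is equally misplaced.* It is post-treatment, but Hypothesis 4 predicts no group difference on it and IV.B.10 ties the rating to clinical outcome, so it is defensible as a precision covariate.

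**Conclusion.** The point holds as a mismatch between hypothesis and model, and it is minor. Under the protocol's own predictions the planned group term is the difference at equal CUAMI-SF change, not the advantage that H6 states. That conclusion rests on the text alone.

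The size rests on assumptions and is unknown. At the more plausible 0.1 SD group difference in CUAMI-SF change, the estimate falls from 0.50 to between 0.44 and 0.48 SD, and power is about unchanged or higher. The direction also depends on Hypothesis 5: with no group difference in CUAMI-SF change there is no shrinkage, and with FEAST worse the term understates reported harm.

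**What to change.** In the Hypothesis 6 paragraph of IV.B.15:
- Make the primary ANCOVA site, treatment group, age and percentage change in HRSD24, without percentage change in CUAMI-SF. Baseline CUAMI-SF, already collected, may be added as an optional pre-treatment covariate.
- Keep the current model as a secondary analysis, described as the group difference at equal CUAMI-SF change and not as a causal effect.
- Report the primary model without percentage change in HRSD24 as a sensitivity check, since that is also post-treatment.
- State that the estimate remains open to confounding and expectation bias, because the groups are non-randomised and unmasked (IV.B.1).

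The cost is wording and one or two extra model runs, with no new data. Power can fall if the groups barely differ on CUAMI-SF change: with HRSD24 change in both models, from 0.74 to 0.64 at 0.1 SD and r = 0.6. The sensitivity run has power of about 0.60 against 0.64 under the assumed 0.3 correlation.
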